## 6. Trial endpoints

Clinical endpoints will be analyzed in all subjects who are enrolled, regardless of whether the trial treatment administered successfully completed for the desired duration. A subject will be considered enrolled in the trial when he/she is randomized to one of the treatment arms of the study. All endpoints are subject-based unless otherwise specified.

The primary endpoint is subject-based of the longer of a 12-month or end of study treatment endpoint of the first occurrence of index limb arterial occlusion, surgical intervention,

endovascular intervention, amputation of the affected limb (primary patency and limb salvage), MI, ischemic stroke or death (survival)

The secondary endpoints are subject-based on the longer of a 12-month or end of study treatment endpoints that include: (a) the first occurrence of any individual component of the primary endpoint, (b) the first occurrence of the following during follow-up: cardiovascular death, or MI, or ischemic stroke, or any amputation above the ankle and (c) severe bleeding defined according to the Global Utilization of Streptokinase and Tissue plasminogen activator for Occluded coronary arteries (GUSTO) classification

The tertiary endpoint is based on the longer of a12-month or end of study treatment moderate bleeding according to the GUSTO classification

Clinically indicated DAPT duration will be based on the longest pre-discharge following index peripheral intervention procedure DAPT duration. This will be determined based on: peripheral intervention device IFUs, preceding coronary intervention, acute coronary syndrome or other guideline-based clinical or device specific DAPT duration.

Study treatment will be discontinued at the first occurrence of a primary endpoint as defined in the table below. Patients, however, can resume taking aspirin, Clopidogrel, or both based on their provider's clinical decision.

Primary endpoint definition(s)	Secondary/Tertiary endpoint definition(s)
Occlusion of the target limb documented by any imaging procedure performed clinically	As described in section 6, except for:
any maging procedure performed ennearly	GUSTO bleeding criteria:
Any surgical or endovascular	1. Severe or Life-threatening: Intracerebral hemorrhage resulting in substantial
revascularization procedure on the index limb	hemodynamic compromise requiring treatment
Amputation above the ankle of the index	2. Moderate: Requiring blood transfusion but not resulting in hemodynamic

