limb Death from any cause	compromise
Ischemic stroke: An episode of neurological dysfunction caused by focal cerebral, spinal, or retinal infarction confirmed by a neurologist	3. Mild: Bleeding that does not meet above criteria
MI: Detection of a rise in cardiac troponin	
(cTn) with at least one value 3x above the	
99th percentile upper reference limit (URL) and with at least 1 of the following:	
Symptoms of ischemia	
• New or presumed new significant ( $\geq 1$	
mm) ST- segment–T wave (ST–T)	
changes or new left bundle branch block (LBBB)	

• Development of pathological Q waves in the ECG	
--	--

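### Non-fatal hemorrhagic stroke is outside every composite and, as the severe-bleeding grade is printed, can fall outside every endpoint

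*Combined protocol and SAP*

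**What the plan says.** Section 6 (Trial endpoints) names stroke in three places, each time as ischemic stroke only.

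- The primary composite closes with "endovascular intervention, amputation of the affected limb (primary patency and limb salvage), MI, ischemic stroke or death (survival".
- Secondary (a) is "a) the first occurrence of any individual component of the primary endpoint", so it inherits the restriction.
- Secondary (b), the cardiovascular composite, is "the first occurrence of the following during follow-up: cardiovascular death, or MI, or ischemic stroke, or any amputation above the ankle".

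The definition table in section 6 describes ischemic stroke as "An episode of neurological dysfunction caused by focal cerebral, spinal, or retinal infarction confirmed by a neurologist". There is no definition of hemorrhagic stroke or of stroke of undetermined type.

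Bleeding is handled separately. Severe bleeding is secondary (c) and moderate bleeding is the tertiary endpoint, both by the GUSTO classification. The table prints the severe grade over two lines, "Severe or Life-threatening: Intracerebral hemorrhage resulting in substantial" and then "hemodynamic compromise requiring treatment". The next grade is "2. Moderate: Requiring blood transfusion but not resulting in hemodynamic" compromise, and the last is "3. Mild: Bleeding that does not meet above criteria". Mild bleeding is not an endpoint.

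Elsewhere, section 23 has all adverse events reported and analyzed, and lists GUSTO bleeding and any hospitalization among expected serious events. In section 24, the DSMB reviews all adverse events every six months, and the CEC's list of events to adjudicate includes strokes of every type as well as bleeding.

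**The concern.** The trial compares longer with shorter dual antiplatelet therapy. The protocol treats bleeding as a recognized hazard of these drugs: section 24 lists both stroke and hemorrhage among the risks, and a history of intracerebral bleeding is an exclusion. A composite that counts strokes caused by infarction but not non-fatal strokes caused by bleeding can record strokes prevented without recording strokes caused. If longer therapy raises hemorrhagic stroke, that asymmetry favors the test arm.

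A separate bleeding endpoint would normally balance this. Here the balance depends on the printed severe grade. If hemodynamic compromise is a condition for intracerebral hemorrhage to be severe, some disabling strokes drop to the residual grade and no pre-specified endpoint compares them by arm. Sections 19 and 20 contain no analysis of stroke by type.

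**Working it through.** **1. Tracing a hemorrhagic stroke through the endpoints (section 6, as printed)**

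| Event | Primary | Secondary (b) | Severe bleeding (c) | Moderate bleeding (tertiary) |
|---|---|---|---|---|
| Fatal | Yes, as death | If classed as cardiovascular death | If it meets the grade | If it meets the grade |
| Non-fatal intracerebral, with compromise needing treatment | No | No | Yes | No |
| Non-fatal, transfused, no compromise | No | No | No | Yes |
| Non-fatal, neither | No | No | No | No (mild) |

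Secondary (a) follows the primary: death counts, hemorrhagic stroke does not. The last row is the gap. Its breadth depends on reading the two printed lines of the severe grade as one condition. If any intracerebral hemorrhage is meant to be severe, intracerebral events in that row move to (c), but they stay outside both composites.

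The literal reading has a further consequence. A bleed outside the brain tissue with hemodynamic compromise and transfusion is not severe (not intracerebral) and not moderate (compromise is present), so it becomes mild. That is an unlikely intention and a reason to have the wording confirmed.

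**2. The plan's own sample size, for reference**

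Inputs (sections 7, 14 and 20): 49% v 34%, 80% power, two-sided 0.05, 10% dropout; 368 evaluable (184 per arm), 404 randomized.

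- Without continuity correction: n = [1.96√(2 × 0.415 × 0.585) + 0.8416√(0.49 × 0.51 + 0.34 × 0.66)]² / 0.15² = 168.2, so 169 per arm.
- With continuity correction: (168.2/4) × [1 + √(1 + 4/(168.2 × 0.15))]² = 181.3, so 182 per arm, 364 in total (plan: 368).
- Dropout: 182/0.90 = 202.2, so 203 per arm, 406 in total (plan: 404).

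The plan's figure reproduces closely and is not in dispute.

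**3. How many events, and what they would do to power**

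The documents give no hemorrhagic stroke rate. Assume 12-month non-fatal rates of 0.2% to 0.5% in control and 0.2% to 1.5% in test.

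- Expected per 184 patients, control: 184 × 0.002 = 0.37 to 184 × 0.005 = 0.92.
- Expected per 184 patients, test: 184 × 0.002 = 0.37 to 184 × 0.015 = 2.76.

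If these were added to the primary composite, independently of its other components, the rates would be 0.49 + h_c × 0.51 and 0.34 + h_t × 0.66.

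| Assumed control / test rate | Composite rates | Power at 184 per arm (no continuity correction) |
|---|---|---|
| none added | 49.0% v 34.0% | 83.4% |
| 0.2% / 0.2% | 49.1% v 34.1% | 83.3% |
| 0.5% / 1.5% | 49.3% v 35.0% | 79.4% |

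**4. Sensitivity of composite (b), illustration only**

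All counts are assumed. Start from 20 control v 18 test subjects of 202 per arm (9.9% v 8.9%): relative risk 18/20 = 0.90, approximate 95% CI 0.49 to 1.65. Then add subjects whose only event is a non-fatal hemorrhagic stroke of any severity.

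| Added, control v test | Total | Relative reduction |
|---|---|---|
| 0 v 0 | 20 v 18 | 10% |
| 1 v 1 | 21 v 19 | 1 − 19/21 = 9.5% |
| 1 v 2 | 21 v 20 | 1 − 20/21 = 4.8% |
| 1 v 3 | 21 v 21 | 0% |

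A few events can move the point estimate of a sparse composite, but the starting contrast is no evidence of benefit in any row.

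**The case against.** The restriction matches the stated aim. The synopsis objective and sections 4 and 5 name ischemic stroke, and an ischemic efficacy composite beside a separate bleeding endpoint is a coherent structure. This stands, and it is why neither composite should be redefined.

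A reader might infer that the composites ignore all hemorrhagic strokes. They do not: fatal ones count as death in the primary and can count as cardiovascular death in (b).

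A reader might also infer that the stroke data go unused and a harm is hidden. The documents do not support that. Adverse events are recorded and analyzed, the DSMB reviews them, and the CEC adjudicates every stroke. What is missing is a pre-specified comparison by arm.

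The strongest objection concerns the severe grade. The endpoint claims to follow the GUSTO classification, the table is only a short summary of it, and the literal reading gives odd results for other bleeds, so a word may simply be missing. That is a fair point: if so, the no-endpoint conclusion falls for intracerebral hemorrhage. The one-sided stroke component remains, and the table still needs correcting.

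Finally, the 1 v 3 row in the illustration cancels the difference exactly because its counts were chosen to do so. It shows sensitivity, not a prediction.

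**Conclusion.** The point holds as a gap in benefit-risk reporting that is cheap to close. On the printed text, non-fatal hemorrhagic strokes are outside the primary, secondary (a) and secondary (b), and those with neither hemodynamic compromise nor transfusion are outside every endpoint. The first part follows directly from the definitions. The second depends on the severe-bleeding wording meaning what it appears to say.

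The number of events is probably small, about 0.4 to 2.8 per 184 patients on assumed rates, and any bias toward the test arm requires that longer therapy raises hemorrhagic stroke, which the documents do not quantify. It would go too far to call the primary test invalid or underpowered on this account: the primary endpoint would stay as it is, so its power is untouched.

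**What to change.** 1. Reconcile the printed severe-bleeding wording in section 6 with the GUSTO classification it invokes, and state whether hemodynamic compromise is meant to be a condition for intracerebral hemorrhage.
2. Keep the primary endpoint and composite (b) as they are. For each, pre-specify one companion analysis that substitutes CEC-adjudicated stroke of any type for ischemic stroke, and tabulate ischemic, hemorrhagic and undetermined strokes by arm.

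Cost: no new visits, data collection or sample size, because the CEC already adjudicates all strokes. Short definitions of hemorrhagic and undetermined stroke must be written. One hemorrhage may count in both the any-stroke composite and severe bleeding, which the report should say. The companion results may look slightly less favorable to the test arm.

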## Protocol Synopsis

## ASPiRE Antiplatelet Strategy for Peripheral Arterial Interventions for Revascularization of Lower Extremities

PI	Name: [name]
	[contact]
	Email: [contact]
TRIAL OBJECTIVE	
Primary Objective	To evaluate whether clopidogrel 75 mg daily on a background of aspirin 81 mg/d for U.S. sites (75-100 mg/d for international sites) for clinically indicated duration or an additional 12 months will lead to an increased rate of primary patency, limb salvage, non-fatal myocardial infarction (MI), ischemic stroke, and survival, in patients receiving endovascular treatment of PAD at end of study treatment
Control Arm	clopidogrel 75 mg daily on a background of aspirin 81 mg/d for U.S. sites (75-100 mg/d for international sites) for clinically indicated duration with a minimum of 30 days.
Test Arm (as applicable)	clopidogrel 75 mg daily on a background of aspirin 81 mg/d for U.S. sites (75-100 mg/d for international sites) for clinically indicated duration + 12 months
Endovascular	Iliac
interventions included	Femoropoliteal
	Below-the knee
TRIAL DESIGN	
Trial Design	Prospective, two-arm, multicenter randomized clinical trial.
PlannedNumber of Subjects	202 subjects will be enrolled in each arm (total subjects = 404)
Clinically indicated dual	Clinically indicated DAPT duration will be based on the longest pre-
antiplatelet therapy	discharge following an index peripheral intervention procedure,
(DAPT) duration	DAPT duration. This will be determined based on: peripheral
	intervention device IFUs, preceding coronary intervention, acute
	coronary syndrome or other guideline-based clinical or device

	specific DAPT durations.
PlannedNumber of Sites / Countries	Approximately 18 investigational centers in the U.S are expected to participate.
	No center will be allowed to enroll more than 40% of planned total enrollment.
Primary Endpoint	Primary Endpoint (subject-based): The first occurrence of index limb arterial occlusion, surgical intervention, endovascular intervention, amputation of the affected limb (vessel occlusion or failure), MI, ischemic stroke or death at 12 months from index procedure or end of study treatment, whichever is longer
Secondary Endpoints	Secondary Endpoints through end of study treatment:
	• The first occurrence of any individual component of the primary endpoint

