	• First occurrence of the following during follow-up: cardiovascular death, or MI, or ischemic stroke, or any amputation above the ankle.
	• Severe bleeding defined according to the Global Utilization of Streptokinase and Tissue plasminogen activator for Occluded coronary arteries (GUSTO) classification
Tertiary Endpoints	• Moderate bleeding defined according to the Global Utilization of Streptokinase and Tissue plasminogen activator for Occluded coronary arteries (GUSTO) classification
Randomization	
 
Patients scheduled for a planned discharge will be randomized on a 1:1 basis using a computerized central randomization portal available through RedCap® to either of the following treatment groups:         
 
ASA (81 mg U.S. sites; 75-100 mg international sites) + clopidogrel: for clinically indicated duration (control arm)
 
ASA (81 mg U.S. sites; 75-100 mg international sites) + Clopidogrel 75mg: for clinically indicated duration +12m (treatment arm)
 
 
 
Randomization will be performed at the within 2 weeks of an eligible procedure
 

Follow-up schedule	All potential subjects will be evaluated for enrollment after the index procedure pre-discharge or within 14 days of the procedure. Follow- up schedule will include patient visits at 30 days and q6 months till the end of study treatment The trial will be considered complete with regard to the primary endpoint after all enrolled subjects have

	completed a 12-month or end of study treatment follow-up evaluation, have died, have a documented premature discontinuation, or whose follow-up window has closed. Follow-up window is $\pm 7$ days for the 30-day visit and $\pm 15$ days for all other visits.

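### The observation window for secondary and tertiary endpoints is stated inconsistently and, even under Section 6, is always longer in the test arm

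*Combined protocol and SAP*

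**What the plan says.** **Window.** In the Synopsis the primary endpoint is read "at 12 months from index procedure or end of study treatment, whichever is longer". The next row is headed "Secondary Endpoints through end of study treatment", with no 12-month minimum. Under that heading one item uses different wording: "First occurrence of the following during follow-up: cardiovascular death, or MI, or ischemic stroke, or any amputation above the ankle". Moderate bleeding, the tertiary endpoint, has no window in the Synopsis.

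Section 6 differs from the heading: "The secondary endpoints are subject-based on the longer of a 12-month or end of study treatment endpoints", and "The tertiary endpoint is based on the longer of a12-month or end of study treatment moderate bleeding". The Synopsis sample-size row and Section 14 also follow subjects for the longer of the two periods.

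**Treatment length.** Control treatment is given "for clinically indicated duration with a minimum of 30 days". Test treatment is the indicated duration plus 12 months.

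**Visits.** The Synopsis "schedule will include patient visits at 30 days and q6 months till the" end of study treatment. Table 2 in Section 12 shows a 12-month visit.

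**Early stopping.** Section 6 states: "Study treatment will be discontinued at the first occurrence of a primary endpoint as defined in the table below". No section defines the end of study treatment for a subject who stops this way.

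**Analysis.** Section 19 compares discrete variables by chi-square. Section 20 promises Kaplan-Meier plots for clinical outcomes, and Section 16 allows models for censored data where appropriate. No time-to-event test is assigned to the secondary or tertiary endpoints.

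**The concern.** Severe and moderate bleeding are the main safety comparison in a trial of longer dual antiplatelet therapy, and the composite of cardiovascular death, MI, ischemic stroke and major amputation is its main hard-outcome comparison. Both need the same calendar of risk in each arm. If the window follows treatment length, the arm treated longer is also watched longer, and a crude proportion cannot separate a drug effect from extra observation time. The bias overstates bleeding in the test arm and hides benefit on ischemic events.

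Two definitions of the window also let sites collect, and analysts count, different data. Follow-up that was never collected may not be recoverable.

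**Working it through.** **The plan's own figure.** The plan gives no event rate or sample size for secondary or bleeding endpoints. Its one sample-size figure is for the primary endpoint. With 49% vs 34%, 80% power, two-sided 0.05 and a continuity correction, 182 per arm are needed, 364 in total; 364 / 0.90 = 404.4. That agrees closely with the stated 368 evaluable and 404 randomized. This point does not affect it.

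**Step 1: windows.** Let D be the indicated duration in months, counted from the index procedure (a simplification). Treatment ends at D in control and at D + 12 in test.
- Synopsis heading: D vs D + 12.
- Section 6: max(12, D) vs D + 12.

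| D | Synopsis heading, control vs test (ratio) | Section 6, control vs test (ratio) |
|---|---|---|
| 30 days | about 1 vs 13 (13.2) | 12 vs 13 (1.08) |
| 3 months | 3 vs 15 (5.0) | 12 vs 15 (1.25) |
| 6 months | 6 vs 18 (3.0) | 12 vs 18 (1.5) |
| 12 months | 12 vs 24 (2.0) | 12 vs 24 (2.0) |

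Section 6 removes the 30-day truncation. It does not equalise the arms for any D.

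**Step 2: counted risk with no treatment effect.** Assume the same constant hazard in both arms and a 12-month risk p of 2%, 5% or 10%; these rates are assumptions. The risk counted over m months is 1 − (1 − p)^(m/12). For D = 6 under Section 6 with p = 5%, control is 5.0% and test is 1 − 0.95^1.5 = 7.4%. With 202 per arm that is 10.1 vs 15.0 expected subjects with an event.

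**Step 3: chance of a spurious significant excess in the test arm.** With n = 202 per arm, p̄ the mean of the two risks and z = 1.96, use the normal approximation Φ{[(p₂ − p₁)√n − z√(2p̄(1 − p̄))] / √(p₁(1 − p₁) + p₂(1 − p₂))}. The nominal value in this direction is 2.5%. The formula is rough for rare events, and it takes one D for everyone and no dropout. Cells show control vs test risk, with that chance in brackets.

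| Rule and D | p = 2% | p = 5% | p = 10% |
|---|---|---|---|
| Section 6, 30 days | 2.0 vs 2.2% (3%) | 5.0 vs 5.4% (4%) | 10.0 vs 10.8% (4%) |
| Section 6, 6 months | 2.0 vs 3.0% (9%) | 5.0 vs 7.4% (17%) | 10.0 vs 14.6% (29%) |
| Section 6, 12 months | 2.0 vs 4.0% (21%) | 5.0 vs 9.75% (45%) | 10.0 vs 19.0% (73%) |
| Synopsis heading, 30 days | 0.17 vs 2.2% (46%) | 0.42 vs 5.4% (85%) | 0.86 vs 10.8% (99%) |

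**Step 4: early stopping.** Suppose a subject has an index-limb revascularisation at month 3 and study treatment stops. If end of study treatment means the actual stop date, the Synopsis heading closes the window at month 3, while Section 6 keeps it open to month 12. If it means the end of the assigned duration, neither rule closes it at the event. The text does not say which meaning applies.

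**The case against.** **The Synopsis heading is an outlier.** Section 6, Section 14 and the Synopsis sample-size row all use the longer-of rule, one Synopsis item counts events during follow-up, and Table 2 has a 12-month visit with adverse-event assessment. This stands. A reader might infer that control subjects are watched for secondary endpoints for only 30 days; that follows from one heading at the minimum duration and is not the plan's general rule. But both texts are current and no precedence is stated. The Synopsis completion rule names a 12-month or end-of-treatment evaluation without saying which governs, and the Appendix makes the length of the questionnaire schedule depend on the arm.

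**Stopping treatment is not stopping follow-up.** This also stands. At the planned rates 202 × 0.49 + 202 × 0.34 ≈ 168 of 404 subjects have a primary event, and a reader might infer that all the survivors then leave observation. The documents do not support that. Section 6 analyses all enrolled subjects whether or not treatment was completed. Table 2 footnote 3 ties the end-of-treatment visit to completing the assigned duration. Section 11 does not list a primary event among its potential reasons for discontinuation. What remains is that no sentence expressly says follow-up continues.

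**Censoring methods are available.** Section 16 and the Kaplan-Meier plots point that way, and a time-to-event comparison over the shared period would remove most of the problem. However, the stated test for discrete outcomes is chi-square, which ignores time at risk.

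**Longer exposure is the strategy under test.** Bleeding in the added months is a true consequence of longer therapy. But control subjects also bleed in those months, and their events are not counted.

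**Conclusion.** The point holds as a conflict in the window definition and as an inequality between arms that remains after the conflict is settled in favour of Section 6. Under Section 6 the distortion is small at a 30-day indicated duration (12 vs 13 months), material at 6 months (12 vs 18) and large at 12 months (12 vs 24). Its overall size depends on the mix of indicated durations and on the event rates, neither of which the documents give; the risks above rest on an assumed constant, equal hazard. The 1 vs 13 month contrast belongs only to a literal reading of the Synopsis heading at the 30-day minimum and should not be taken as expected behaviour. Loss of events after a first primary event is a risk created by an undefined term, not something the plan prescribes. The primary sample size is unaffected.

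**What to change.** 1. Align the Synopsis heading with Section 6, and in both places state one observation window for all secondary and tertiary endpoints, identical in both arms. Two options:
   - A fixed time from the index procedure.
   - Each subject's indicated duration plus 12 months, whichever arm the subject is in. For this option the indicated duration should be recorded before randomization.
2. In Section 19, compare the arms over that common window with time-to-event methods in place of crude proportions.
3. Define end of study treatment for subjects who stop early, and state that follow-up continues to the common date after a non-fatal primary event or the end of treatment.

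The rule on stopping treatment is unchanged.

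**Cost.** Mostly wording. With the second option, or a fixed time beyond 12 months, some control and post-event subjects stay longer in the existing visit or phone schedule. A 12-month cut needs little extra follow-up but leaves later test-arm events out of the comparison. Since assigned treatment differs only after the indicated duration, a 12-month cut would also hold no treatment contrast for a subject whose indicated duration is 12 months.

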#### **Secondary Endpoints**

Secondary endpoints will be summarized at the specified time points using the descriptive statistics described above, individually or in comparison between the treatment groups. Statistical analyses of the following secondary endpoints will be summarized for descriptive purposes and without adjustments for multiplicity:

- Changes in ABI from baseline to hospital discharge, 30 days, 6 months and 12 months post-procedure will be analyzed using paired two-sided Student *t*-tests.
- Changes in Walking Impairment Questionnaire scores from baseline to 30 days, 6 month, and 12 months post-procedure will be analyzed using paired two-sided Student *t*-tests.
- Freedom from Target Lesion Revascularization Kaplan-Meier estimates and plots will be presented to 12 months post-procedure

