## **23.Adverse Events**

All Adverse Events (AE) and Serious Adverse Events (SAE) will be reported through EDC and analyzed through study follow-up period.

Term	Definition
Adverse Event (AE)	Any untoward medical occurrence in a subject. This definition does not imply that there is a relationship between the adverse event and the treatment under investigation.
	Note 1: In addition, the definition of AE applies to any event with an onset post- randomization procedure or to any underlying diseases, present at baseline, that exacerbate in severity post- randomization procedure. Therefore, any underlying disease that was present at the time of enrollment is not to be reported as an AE, but any increase in the severity in the underlying disease is to be reported as an AE. This definition includes events occurring in the follow-up period.
Serious Adverse Event (SAE)	
 
An adverse event that:
 
led to death;
 
led to a serious deterioration in the health of the subject that: 
 
resulted in a life-threatening illness or injury,
 
resulted in a permanent impairment of a body structure or a body function,
 
 
 

Clinical events to be considered and reported as expected SAE include, but are not limited to:

- MAE (see definitions)
- Stent Thrombosis
- Bleeding complication as per GUSTO definition
- Vascular event requiring target limb surgical or endovascular intervention or amputation
- Any hospitalization

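### As printed, the section 6 bleeding table grades a non-cerebral bleed with haemodynamic compromise as mild, so it counts in neither bleeding endpoint

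*Combined protocol and SAP*

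**What the plan says.** The Synopsis lists as a secondary endpoint "Severe bleeding defined according to the Global Utilization of Streptokinase and Tissue plasminogen activator for Occluded coronary arteries (GUSTO) classification". Section 6 repeats this as secondary endpoint (c) and makes GUSTO moderate bleeding the tertiary endpoint. Mild bleeding is in no endpoint.

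The grades are spelled out once, in the right-hand column of the section 6 definition table, under a heading that names the GUSTO criteria:

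- Severe: "Severe or Life-threatening: Intracerebral hemorrhage resulting in substantial", continued on the next line as "hemodynamic compromise requiring treatment".
- Moderate: "Moderate: Requiring blood transfusion but not resulting in hemodynamic", completed on the next line by the word compromise.
- Mild: "Mild: Bleeding that does not meet above criteria".

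Section 23 lists "Bleeding complication as per GUSTO definition" among expected serious adverse events but gives no second set of grades. Section 24 assigns adjudication of bleeding events to the CEC under a charter that is not part of the documents.

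**The concern.** The moderate line excludes any bleed with haemodynamic compromise. That makes sense only if such bleeds belong to a higher grade, yet the severe line admits them only when they are intracerebral. A non-cerebral bleed with compromise fits neither line and drops to the residual category, below a less serious bleed.

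The trial compares a clinically indicated course of dual antiplatelet therapy with the same course plus 12 months. Bleeding is an obvious harm to compare, and section 24 itself lists gastrointestinal bleeding among the risks of the study drugs. If the printed table is followed, non-cerebral bleeds with haemodynamic compromise disappear from the trial's only two bleeding endpoints.

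**Working it through.** No published figure is to be reproduced here; the point rests on the definitions alone.

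**Inputs (section 6 table).** Three yes/no facts decide the grade: whether the bleed is intracerebral, whether there is haemodynamic compromise, and whether blood was transfused. This grid treats the compromise named in the severe line and in the moderate line as one threshold.

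**Rules as printed.**
- Severe = intracerebral AND compromise.
- Moderate = transfused AND no compromise.
- Mild = all else.

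**Alternative rule, for the possibility that an 'or' was lost.** Severe = intracerebral OR compromise. Moderate is then any remaining bleed that is transfused without compromise, and mild is the rest.

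| Site | Compromise | Transfused | As printed | With 'or' |
|---|---|---|---|---|
| Other | no | no | mild | mild |
| Other | no | yes | moderate | moderate |
| Other | yes | no | mild | severe |
| Other | yes | yes | mild | severe |
| Intracerebral | no | no | mild | severe |
| Intracerebral | no | yes | moderate | severe |
| Intracerebral | yes | no | severe | severe |
| Intracerebral | yes | yes | severe | severe |

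**Counts.**
- As printed: 2 severe + 2 moderate + 4 mild = 8. Among the 4 non-cerebral rows: 0 severe, 1 moderate, 3 mild. Both non-cerebral rows with compromise are mild.
- With 'or': 6 severe + 1 moderate + 1 mild = 8.
- With only the site restriction removed (severe = compromise at any site): 4 severe + 2 moderate + 2 mild = 8.

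**Order check.** Hold site and transfusion fixed and add compromise; the grade should not fall. There are four such pairs:
- other site, not transfused: mild to mild;
- other site, transfused: moderate to mild (a reversal);
- intracerebral, not transfused: mild to severe;
- intracerebral, transfused: moderate to severe.

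That is 1 reversal as printed, and 0 under either alternative rule.

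**If the two thresholds differ.** The severe line speaks of substantial compromise requiring treatment, the moderate line of compromise without qualification. If these are two thresholds, a transfused non-cerebral bleed with lesser compromise is not severe, and is not moderate because compromise is present. It is therefore mild, even with an 'or' restored. The 0 reversals above depend on the one-threshold reading.

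The rows are combinations, not frequencies. Nothing in the documents says how often each would occur.

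**The case against.** The strongest objection is that the printed wording may be neither what the sponsor wrote nor what adjudicators will use. The available text is converted from PDF, and the left column of this table is visibly garbled. The endpoints are defined by reference to GUSTO, and an expert committee working under its own charter may apply the published scale. Part of this stands, and it is why confidence is medium. Against it, the words from intracerebral hemorrhage through substantial sit unbroken on one line, so a lost conjunction looks unlikely. The table presents itself as the GUSTO criteria and is the only definition printed. An adjudicator who applied different wording would be departing from the protocol.

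The second objection is that the consequence is limited, and this stands in full. Section 20 says "Secondary endpoints will be summarized at the specified time points using the descriptive statistics", and bleeding is not among the specific analyses it goes on to list. Bleeds remain reportable under section 23, where the list of expected serious events also includes any hospitalisation. The Data Safety Monitoring Board (DSMB) reviews all adverse events. A fatal bleed counts in the primary endpoint through "Death from any cause". These safeguards protect surveillance; they do not repair the graded comparison between arms.

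**Conclusion.** The concern holds on the text as printed. The grading rule is out of order: a transfused non-cerebral bleed moves from moderate to mild when haemodynamic compromise is added, and no non-cerebral bleed can be severe. Both non-cerebral combinations with compromise fall outside the secondary and tertiary bleeding endpoints. By the same wording, an intracerebral haemorrhage with neither compromise nor transfusion is mild; the documents do not show whether that is intended.

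The effect is confined to the graded bleeding endpoints. The primary analysis and the sample size do not depend on it. How many patients would be misgraded, and in which arm, cannot be estimated from the documents.

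The conclusion assumes that the severe line is as the sponsor wrote it and that the table governs adjudication. If the source file shows an 'or' after intracerebral hemorrhage, the main fault disappears, and only the question of one or two compromise thresholds would remain. This should be corrected, but it does not threaten the trial's main conclusion.

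**What to change.** 1. Check the severe line of the section 6 table against the source file.
2. If it stands, reconcile the table with the GUSTO classification the protocol cites. The result should not confine severe to intracerebral bleeds, and should not let a bleed with substantial compromise requiring treatment rank below a transfused bleed without compromise. Take the grade of intracerebral haemorrhage without compromise from that classification, and add no wording that departs from it.
3. While doing so, state whether the compromise named in the severe and moderate lines is one threshold or two.
4. Align the CEC charter with the corrected table.
5. If any bleeds have already been adjudicated, have them re-graded and say by whom. Section 24 gives bleeding events to the CEC, whereas the Appendix on the walking impairment score gives clinical adjudication to the safety monitoring board.

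The cost is one or two lines in the table, a charter check and a small amount of re-adjudication if any is needed. Re-grading is possible only if compromise and transfusion are recorded in the case report form or source documents. Section 23 requires an event description including the action taken, and Table 2 schedules adverse event assessment at every follow-up visit, but the documents do not show the form's fields.
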